3.1.2 Baseline Lead-in Period

Eligible subjects will enter a placebo Baseline Lead-in Period. This 14 day period allows subjects to get accustomed to being in a clinical trial (e.g. avoiding prohibited medications) and taking investigational medicinal product (IMP) on a regular basis. This period also provides an opportunity to develop a more accurate assessment of adrenal steroids and steroid intermediates and documentation of exogenous steroid replacement therapy (GC and MC).

In order to obtain unbiased information, the subjects will not know that the tablets received are placebo and do not contain active drug substance (ATR-101). Placebo tablets for this period will look identical to ATR-101 125 mg tablets (i.e. Dose Level 1). However, the study center personnel will be aware that the tablets are placebo.

At the conclusion of the Baseline Lead-in Period, subjects will be assessed for protocol compliance, including IMP compliance (tablet counts) and whether it is appropriate to proceed in the study.

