3.1.6 Follow-up Visit

Two weeks after the Final Study Visit or Early Termination Visit, a Follow-up Visit will take place. This will consist of a telephone interview with the subject to determine if any safety events need to be reported and to record concomitant medications, especially GC and MC.

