6.12 Adverse Events, Serious Adverse Events, and Reporting

6.12.1 Adverse Events, Severity, and Relationship

Adverse Event (AE): Any untoward medical occurrence in a subject or clinical investigation subject administered an investigational product. An AE does not necessarily have a causal relationship with IMP.

- All AEs reported for enrolled subjects during the clinical study will be recorded on the eCRF. All AEs, regardless of relationship to study drug or procedure, should be collected beginning from the time the subject signs the study consent. AEs in clinical investigation subjects include any change in the subject's condition. This includes symptoms, physical findings, or clinical syndromes.
- An abnormal laboratory value may be considered an AE if the identified laboratory abnormality leads to any type of intervention whether prescribed in the protocol or not. It is up to the PI/SI to determine whether an abnormal laboratory value constitutes an AE. If an abnormal laboratory value is caused by a disease process, the disease process and not the laboratory abnormality should be listed as the AE (e.g., if new onset viral hepatitis is causing elevated alanine aminotransferase (ALT), hepatitis and not the elevated ALT should be listed as the AE).
- Examples of laboratory abnormalities that should be considered AEs include those that result in withdrawal of the study treatment, withholding study treatment pending some investigational outcome, or additional concomitant treatment. All laboratory abnormalities considered to constitute an AE should be recorded on the appropriate AE page of the eCRF. Laboratory abnormalities do not need to be listed as separate AEs if they are considered to be part of a clinical syndrome that is being reported as an AE. It is the responsibility of the Investigator to review all laboratory findings in all subjects. Abnormal values should be commented upon as to clinical relevance or importance on the eCRF or the laboratory report as appropriate. Medical and scientific judgment should be exercised in deciding whether an isolated laboratory abnormality should be classified as an AE.
- AEs will be collected from the time the subject signs informed consent until 30 days after last dose of IMP.
- Every effort must be made by the PI/SI to categorize each AE according to its severity and its relationship to IMP.
- Subjects who develop toxicity on study will be followed until the event resolves, stabilizes or returns to baseline.

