7.8 Follow-up Visit

Two weeks after completion of the Final Study Visit or Early Termination Visit, the PI, SI or other qualified medical personnel from the study center will contact the subject. A telephone interview will take place to confirm the status of the subject. Any safety events will be reported and concomitant medications, including replacement steroids will be recorded. This telephone interview will conclude the subject's study participation.

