## 5.2 Treatments Administered and Blinding

During the 14-day Baseline Lead-in Period, placebo tablets that match the ATR-101 125 mg tablets will be administered BID.

Starting with Dose Level 1, each dose level will consist of a 28-day dosing regimen consisting of 14 days of ATR-101 treatment followed immediately by 14 days of matching placebo washout.

Subjects will be blinded to treatment beginning with the Baseline Lead-in Period, which will use placebo tablets that appear identical to ATR-101 125 mg. Dose levels 1 to 5 are split into two weeks of active treatment (ATR-101) followed by two weeks of treatment with matching placebo (Washout Period).

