### **6.2 General Considerations**

Unless otherwise specified, summaries will be presented by dose level where the first dose of ATR-101 defines the start of each dose level. In other words, each dose level consists of Day 1 – Day 28 (2 weeks of ATR-101 and 2 weeks of Placebo). Subjects may be counted in more than one dose level. Each subject will be counted once in each dose level according to sequential participation and once in the overall column.

In addition, summaries will be provided by last dose level. In other words, the results from the subject's last completed dose level will be carried forward.

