### **6.11.1 Adverse Events**

AEs will be coded and classified by system organ class and preferred term using the Medical Dictionary for Regulatory Activities (MedDRA). All AEs reported for enrolled subjects during the clinical study will be recorded on the electronic case report form (eCRF). All AEs, regardless of relationship to study drug or procedure, should be collected beginning from the time the subject signs the study consent. AEs in clinical investigation subjects include any change in the subject's condition. This includes symptoms, physical findings, or clinical syndromes.

TEAEs are defined as adverse events that happen for the first time on or after the first dose date (Dose Level 1 Day 1) of ATR-101.

An overview with counts of events and subjects will be provided by dose level and treatment at AE onset and overall for the incidence of AEs in the following categories:

- Any TEAE
- Maximum severity of TEAE
- Any study drug related TEAE
- Maximum severity of study drug related TEAE
- Any serious treatment-emergent SAE (TESAE)
- Any study drug related SAE
- Death due to AE
- AE leading to discontinuation from study
- Study drug related AE leading to discontinuation from study

The incidence of TEAEs will be summarized by dose level and treatment at AE onset and overall by system organ class and preferred term. System organ class will be sorted alphabetically and preferred term will be sorted by descending total frequency within system organ class. Similar summaries will be provided for TEAEs by maximum severity. The same summaries will be done for study drug related TEAEs.

The AE summaries will be provided by dose level and treatment at AE onset. In other words, AEs starting on or after ATR-101 and prior to the subsequent Placebo dose will be attributed

to ATR-101. AEs starting on or after Placebo and prior to the subsequent ATR-101 dose will be attributed to Placebo.

Listings will be provided for any SAEs, AEs leading to discontinuation from study, and AEs beginning in the Placebo Baseline Lead-In Period.

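### The SAP gives the washout Placebo AE window no end at a subject's last dose level, so follow-up events count as Placebo over about 29 to 44 days, against 14 days on ATR-101

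*SAP*

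**What the plan says.** SAP 5.2 plans each dose level as "14 days of ATR-101 treatment followed immediately by 14 days of matching placebo washout". SAP 6.11.1 then allocates AEs by treatment at onset. For the active period, "AEs starting on or after ATR-101 and prior to the subsequent Placebo dose will be attributed" to ATR-101. For the washout, "AEs starting on or after Placebo and prior to the subsequent ATR-101 dose will be attributed to Placebo". Neither rule says what happens when the closing dose never comes, and the treatment-emergent definition in the same section has a start but no end.

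SAP 6.2 defines a dose level as Day 1 to Day 28, "2 weeks of ATR-101 and 2 weeks of Placebo", as a default that other sections may override.

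Protocol 6.12.1 sets the collection period: "AEs will be collected from the time the subject signs informed consent until 30 days after last dose of IMP". Placebo counts as IMP: Protocol 3.1.2 describes the placebo lead-in as a time for subjects to get used to "taking investigational medicinal product (IMP) on a regular basis". Protocol 3.1.6 sets the last contact: "Two weeks after the Final Study Visit or Early Termination Visit, a Follow-up Visit will take place". Protocol 7.8 adds: "This telephone interview will conclude the subject's study participation".

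SAP 6.11.1 plans counts of events and of subjects. SAP 6.3.2 sets the denominator for each level and treatment as the subjects with at least one dose there. No person-time measure is planned.

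**The concern.** Every subject who reaches the washout of a final level, whether as a responder or by completing Level 5, has a Placebo window that the SAP does not close. Read literally, all of that subject's off-treatment follow-up falls in the Placebo column for that level. Longer observation yields more events even if neither treatment causes any, and unadjusted counts and percentages cannot show this.

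The trial has no parallel control arm, so ATR-101 against washout Placebo is the only treatment contrast in the AE tables, and safety is part of the primary objective (Protocol 2.1, SAP 3.1). A Placebo column inflated by follow-up time makes ATR-101 look better tolerated than the data warrant. If the cut-off is not written down, someone must choose it later, and Protocol 9.9 says the sponsor is not blinded to the safety results.

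**Working it through.** **Inputs**
- ATR-101 period 14 days and placebo period 14 days (SAP 5.2).
- First placebo dose on Day 15; last placebo dose on Day 28 (SAP Figure 2).
- AE collection to 30 days after the last IMP dose: Day 28 + 30 = Day 58 (Protocol 6.12.1).
- Last scheduled contact: Day 29 + 14 = about Day 43, allowed ±3 days (Protocol 3.1.6 and 6.1).

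**The plan's own figure.** 14 + 14 = 28 days per level, as SAP 6.2 states.

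**Last-level Placebo window.** Length = end day − 15 + 1.

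| End of window | Placebo days | Ratio to 14 ATR-101 days |
|---|---|---|
| Day 28 (SAP 6.2) | 14 | 1.00 |
| Day 43 (telephone call) | 29 | 2.07 |
| Day 58 (30-day rule) | 44 | 3.14 |

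If the call moves within its ±3 days, 29 becomes 26 to 32. If the washout lasts 11 to 17 days, as Protocol 6.1 allows, 44 becomes 41 to 47.

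**Pooled over a subject's levels.** With K levels and last-level window w, Placebo to ATR-101 days = (14(K − 1) + w) / (14K).
- w = 44: 3.14, 2.07, 1.71, 1.54, 1.43 for K = 1 to 5. At K = 5 this is 100 / 70.
- w = 29: 2.07, 1.54, 1.36, 1.27, 1.21. At K = 5 this is 85 / 70.

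**Effect on incidence with no drug effect.** The documents give no AE rate. Assume a constant hazard, the same in both periods, and let p be the chance of at least one AE in 14 days. Over w days the chance is 1 − (1 − p)^(w/14).

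| Assumed p (ATR-101, 14 days) | Last-level Placebo, 29 days | Last-level Placebo, 44 days |
|---|---|---|
| 10% | 20% | 28% |
| 20% | 37% | 50% |
| 30% | 52% | 67% |
| 40% | 65% | 80% |

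**The opposite case.** A subject who stops after d days of ATR-101 and takes no placebo at that level has an ATR-101 window of d + 30 days under the 30-day rule, for example 7 + 30 = 37 days.

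**Which rule governs?** SAP 6.2 yields to more specific text, and 6.11.1 is the specific text for AEs, so the open-ended reading is the more natural one. If 6.2 governs instead, the windows are equal, but an AE after Day 28 of the last level is still treatment-emergent and has no dose-level column.

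**The case against.** The strongest reply is that SAP 6.2 already ends each level at Day 28, that 6.11.1 only splits a level by treatment, and that the inflation is therefore not certain. This stands in part: the two sections conflict, and the inflation follows from one reading of them. It does not remove the problem, because the other reading leaves follow-up events without a place in the tables.

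Second, 44 days is the upper figure. Participation ends at a call about 15 days before the 30-day limit, and events may be captured less completely by one call than by two-weekly visits. This stands, and it is why the range starts at 29 days. The constant-hazard illustration would shrink further if capture in follow-up is poorer.

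Third, the consequence is limited. SAP 6.11 plans no formal safety analysis, there are 9 to 17 subjects, and SAEs and AEs leading to discontinuation are also listed individually. This stands. However, with no formal tests, readers rely on the columns themselves.

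Fourth, assigning late events to the last treatment received is a defensible convention. It is, but here it puts unequal observation time into columns that are read against each other without any time adjustment.

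A reader might also infer an artificial dose trend, because non-responders who complete the study all end at Level 5. The documents do not support that for the ATR-101 columns. SAP 6.11.1 splits each level by treatment, so for subjects who complete the washout the ATR-101 window is 14 days at every level. A last level of 43 to 58 days against 28 would matter only in a column pooling both treatments within a level, which 6.11.1 does not specify.

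**Conclusion.** The point holds for subjects who start the washout at their last dose level. Under SAP 6.11.1 their Placebo window is about 29 to 44 days against 14 on ATR-101, a ratio of 2.1 to 3.1 at that level. Pooled over levels, the ratio is 1.2 to 1.4 for a five-level completer. It is largest for a subject who responds at Level 1, a dose that Protocol 3.2 intends to be non-effective, so the pooled 3.1 should not be taken as typical. Unadjusted Placebo incidence is raised accordingly.

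It would go too far to say that the rule favours ATR-101 for every subject: those who stop on ATR-101 before any placebo at that level carry the extra time on ATR-101.

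The day counts rest on the planned 14-day periods and on placebo counting as IMP. The percentages rest on an assumed constant hazard and show direction and scale only. The primary endpoint and sample size are not touched. The SAP should be corrected, because the rule as written distorts the only treatment contrast in the AE tables and the correction is cheap.

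**What to change.** In SAP 6.11.1:
- End the last-level Placebo window at the end-of-washout visit (Day 29), or at a short, pre-specified interval after the last placebo dose if that is earlier.
- Report later AEs in a separate post-treatment follow-up column that shows the last level and treatment received.
- For subjects who stop on ATR-101 without placebo at that level, put follow-up AEs in the same column, identified as following ATR-101, so that delayed drug effects stay visible.
- Add events per subject-day to the overview by dose level and treatment.

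Reconcile SAP 6.2 with 6.11.1 on where a dose level ends for AE tables. Reconcile Protocol 6.12.1 with 7.8 on whether AE collection ends at the telephone call or at 30 days after the last dose.

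The SAP part costs some wording, one extra column and a person-time denominator. The small downside is that some AEs move out of the treatment columns; none is lost from the report.

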### **6.11.2 Clinical Laboratory Evaluations**

Safety laboratory data (chemistry, hematology, and coagulation) will be summarized by dose level for Day 1 and Day 15 visits. Change from Day 1 to Day 15 will be summarized within each dose level. The change from Day 15 to Day 1 of the next dose level will also be summarized.

The number and frequency of subjects with laboratory abnormalities will be summarized by dose level. Shift tables from Day 1 to Day 15 will be presented for ALT and AST (>1xULN to  $\leq 2$ xULN, >2xULN to  $\leq 3$ xULN, >3xULN) and CK (>1xULN to  $\leq 5$ xULN, >5xULN to  $\leq 10$ xULN, >10xULN). Shift tables from Day 15 to Day 1 of the next dose level will also be presented.

Urinalysis will be summarized overall at Screening and the Final Study Visit.

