5.3.3 Changes in Daily Dose are Not Permitted

Subjects must adhere to the daily dose of IMP according to each dose level. Deviation from the protocol regimen is not permitted. Specifically, lower daily doses are not permitted for any reason. If a subject cannot tolerate a given dose due to a safety issue then early termination from the study is the recommended course of action. Decreasing to a lower dose (e.g., once per day dosing or taking fewer tablets at each AM or PM dose) or to the previous dose level is not permitted. Additionally, increased doses are not permitted at any time other than those associated with the protocol design (i.e. advancing to the next dose level). Taking more tablets at a given dose is not permitted under any circumstances.

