7.7 Early Termination Visit

The Early Termination Visit will occur if a subject is not able to complete the study procedures as detailed in the protocol for any reason. The schedule of events for the Early Termination Visit is identical to the Final Study Visit (See Section 7.6).

- Confirm that the morning dose of replacement steroids (GC/MC) was not taken or if taken confirm the day and time of the last dose
Note: If the morning dose of replacement steroids (GC/MC) was taken, it is acceptable to complete the Final Study Visit
- Confirm the day and time of the last dose of IMP
- Perform drug accountability and confirm compliance with IMP
- Review of concomitant medication

- Assess AEs
- Complete physical examination
- Vital signs (including blood pressure, pulse, respiration, body weight and temperature)
- 12-lead ECG
- Blood sampling for hematology, serum chemistry, PT/aPTT/INR
- Urinalysis
- Urine pregnancy testing (β -hCG) for females who are not surgically sterile or who have not been naturally postmenopausal for at least 12 consecutive months (i.e., who have had menses any time in the preceding 12 consecutive months)
- **Blood sampling for steroids/steroid intermediates (before 10 AM)**
- Blood sampling for exogenous glucocorticoid levels
- Blood sampling for ATR-101 PK assessment (trough levels)

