## **6.11 Safety Analyses**

Safety data includes AEs, physical examinations, vital signs, ECGs, and clinical laboratory assessments. Safety data will be summarized and listed. No formal statistical analysis of the safety data will be conducted. All safety summaries will be based on the Safety Population. Safety summaries will be based on observed values only.

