### **6.11.4 Electrocardiogram**

All subjects will have 12-lead ECG assessments at Screening, Day 1 pre-dose and 2 hours post-dose for each dose level, Day 15 pre-dose for each dose level, and at the completion of the Placebo Washout Period on Day 29 (this ECG could serve as the pre-dose ECG, Day 1, if the subject is moving to the next dose level or as the ECG for the Final Study Visit or Early Termination Visit).

ECG measurements (heart rate, PR, QRS, QT, RR, QTcB, and QTcF) will be summarized by dose level for Day 1 pre-dose, 2 hours post-dose and Day 15 visits. Change from Day 1 pre-dose will be summarized.

ECG interpretations (normal, abnormal not clinically significant, abnormal clinically significant) will be tabulated by dose level for each time point.

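### The ALT/AST/CK shift, ECG-interval and vital-sign tables have no place for the end-of-exposure value of a subject who stops ATR-101 before a Day 15 assessment

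*SAP*

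**What the plan says.** **Laboratory (SAP 6.11.2).** "Safety laboratory data (chemistry, hematology, and coagulation) will be summarized by dose level for Day 1 and Day 15 visits". For the first set of shift tables: "Shift tables from Day 1 to Day 15 will be presented for ALT and AST", with CK on the same two days. For the second set: "Shift tables from Day 15 to Day 1 of the next dose level will also be presented".

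**ECG and vital signs (SAP 6.11.4 and 6.11.3).** ECG intervals, QTcF among them, are "summarized by dose level for Day 1 pre-dose, 2 hours post-dose and Day 15 visits", with change taken from Day 1 pre-dose. Vital signs follow the same pattern, with Day 1 readings pre-dose and at 1, 2 and 4 hours, and a Day 15 reading.

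**Missing values.** SAP 6.11: "Safety summaries will be based on observed values only". Neither SAP 6.2 nor SAP 6.11 maps an Early Termination value to Day 15 or defines a last or worst on-treatment value.

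**Last-level summary (SAP 6.2).** In this additional summary, "the results from the subject's last completed dose level will be carried forward".

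**What happens to an intolerant subject.** Protocol 5.3.3 does not permit dose reduction; if a safety issue makes a dose intolerable, "then early termination from the study is the recommended course of action". Protocol 7.7 adds: "The schedule of events for the Early Termination Visit is identical to the Final Study Visit". That schedule includes chemistry, ECG and vital signs.

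**The concern.** By-level tables of change and shift should show what happened to everyone exposed at that level. Here the on-drug endpoint is a single scheduled visit, and a subject who stops for intolerance may never reach it. Whether the value is missing can then depend on the toxicity that the table is meant to display. Safety is part of the primary objective, and Protocol 9.7 asks for laboratory and ECG changes by dose without restricting them to one visit. If the Day 1 to Day 15 tables are read alone, they may look cleaner than the experience of the subjects dosed.

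**Working it through.** The plan states no figure on this point, so there is none to reproduce. The check sets the provisions side by side; the arithmetic after that is illustrative.

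**Step 1. Is the subject in the level?** Yes. For by-level summaries, SAP 6.3.2 requires only one dose in that level.

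**Step 2. Is an end-of-exposure value collected?** It should be. Protocol 7.7 schedules chemistry, ECG and vital signs at Early Termination.

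**Step 3. Do the tables take that value?**

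| Table | Values needed | Subject with no Day 15 assessment |
|---|---|---|
| ALT/AST/CK shift, first set | Day 1 and Day 15 | No endpoint |
| ALT/AST/CK shift, second set | Day 15 and next level's Day 1 | Neither value |
| ECG intervals | Day 1 (pre-dose, 2 h) and Day 15 | Day 1 values only |
| Vital signs | Day 1 (pre-dose, 1, 2, 4 h) and Day 15 | Day 1 values only |

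The subject keeps the Day 1 post-dose ECG and vital signs. The end-of-exposure value is what is missing.

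**Step 4. Where is the cut-off?** Protocol 6.1 allows the end-of-treatment sample from the 12th day of dosing. The gap is therefore certain only for stops before that day, or where the visit is recorded as Early Termination.

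**Step 5. Does the last-level summary repair it?** No. If it is applied to safety data, a subject who stops during Level 2 to 5 would appear at the earlier level that he or she completed. A subject who stops during Level 1 has no completed level to carry forward.

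**Step 6. Effect of one such case (illustration).** Assume that one subject at a level stops before any Day 15 draw and has ALT above 3xULN at Early Termination, and that nobody else exceeds 3xULN. The sizes are the 9 and 17 subjects of SAP 6.1; intervals are exact (Clopper-Pearson) 95%.

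| Dosed at level | Table as written | With the Early Termination value |
|---|---|---|
| 9 | 0/8 = 0% (0 to 36.9%) | 1/9 = 11.1% (0.3 to 48.2%) |
| 17 | 0/16 = 0% (0 to 20.6%) | 1/17 = 5.9% (0.1 to 28.7%) |

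If the full Safety Population is the denominator, the entries as written are 0/9 and 0/17. The numerator is zero either way.

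**Step 7. Chance of at least one early stop.** The documents give no rate. Assume a probability p per subject, independent between subjects, over a range of 5% to 20%. The chance is 1 − (1 − p)^n:

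| p | n = 9 | n = 17 |
|---|---|---|
| 5% | 1 − 0.95^9 = 37% | 1 − 0.95^17 = 58% |
| 10% | 1 − 0.90^9 = 61% | 1 − 0.90^17 = 83% |
| 20% | 1 − 0.80^9 = 87% | 1 − 0.80^17 = 98% |

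**The case against.** The strongest reply is that no event is hidden. Protocol 6.12.1 treats a laboratory abnormality that leads to withdrawal of treatment as an adverse event. SAP 6.11.1 tabulates AEs by level and treatment at onset, includes a row for discontinuation due to an AE, and lists those cases. SAP 6.11.2 counts laboratory abnormalities by level with no visit restriction. SAP 6.11.5 tabulates physical findings at each visit. ECG interpretations are tabulated at each time point (SAP 6.11.4), which may or may not include the Early Termination ECG. All safety data are also listed.

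This stands, and it defeats a reading that a reader might otherwise infer: that every by-level safety table is confined to Day 1 and Day 15, or that safety would be judged only from subjects who tolerated a full treatment period. The documents do not support either. What they leave open is narrower: an AE term or an abnormality count does not give a by-level ALT shift in multiples of ULN or a change in QTcF.

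A second reply is that the protocol schedules no laboratory tests or ECGs between Day 1 and Day 15. A silent rise would ordinarily be found at the Day 15 draw, which is in the tables. An earlier stop would more likely follow symptoms or need an unscheduled test. This also stands, and it limits how often the gap would matter.

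Third, no safety subsection of the SAP names a last-level table. It would go too far to say that an intolerant subject will be shown with normal values from the previous level. That follows only if the general rule in SAP 6.2 is applied to safety data, which sits uneasily with the observed-values rule in SAP 6.11.

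**Conclusion.** The point holds in a limited form. As written, the ALT/AST/CK shift tables, the ECG-interval changes and the vital-sign changes have no entry for the end-of-exposure value of a subject who stops before a Day 15 assessment or whose visit is recorded as Early Termination. The value should exist, and the subject is in the level's Safety Population. Where the stop is related to toxicity, the omission biases these particular tables toward safety.

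The size is illustrative: one case moves 1/9 to 0/8, or 1/17 to 0/16. That rests on an assumed case, and the 37% to 98% chance of at least one early stop rests on assumed rates of 5% to 20% for stops of any kind, not only those with an abnormal value. The documents do not support a claim that the bias is worst at the higher levels, since they give neither stop rates nor numbers remaining by level. This is an inexpensive improvement to the tables; it does not show that safety events go unreported.

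**What to change.** 1. **Keep** the Day 15 summaries in SAP 6.11.2 to 6.11.4.
2. **Add by level** the worst ALT and AST after the Day 1 ATR-101 dose to the shift tables, together with the maximum QTcF change and the last on-treatment vital signs. Include Early Termination and unscheduled values. Do the same for CK if it is collected; CK is not in the chemistry list of Protocol Table 5, so its source should be stated.
3. **Close the window** at the first placebo dose of that level. For a subject who never starts placebo, close it at a pre-stated number of days after the last ATR-101 dose, and show days since last dose. This second limb is needed because Protocol 6.15 and 7.7 set no maximum interval from last dose to the Early Termination Visit, so an off-drug value could otherwise count as on-treatment.
4. **In SAP 6.2**, state whether the last-level summary applies to safety data. If it does, define it there by the last level started, and reconcile it with the observed-values rule.

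The cost is SAP wording and a little extra programming, with no new visits. Abnormality rates may come out slightly higher because worst values include unscheduled tests.
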